## **Self-Report Measures**

**Demographic and general dental information questionnaire.** See appendix A for specific questions related to demographics and general dental information. The questionnaire will consist of 20-items asking about the participants' age, sex, ethnicity, yearly income, education, employment status, transportation to the dentist, and dental related experiences.

### **Anxiety and Related Disorders Interview Schedule for DSM-5-Adult Version**

**(ADIS-5).** The ADIS-5 is a structured interview conducted by trained professionals that diagnosis current DSM-5 anxiety disorder, however, only the specific phobia section will be used in this study. Previous versions (i.e., ADIS, ADIS-R, & ADIS-IV) have demonstrated good psychometric properties (Brown, Di Nardo, Lehman, & Campbell, 2001; Di Nardo, Moras, Barlow, Rapee, & Brown, 1993). For the current study, The ADIS-5 will be conducted by clinicians in training, and be used in order to describe the study's sample.

**Subjective Units of Distress Scale (SUDS; Wolpe, 1973).** The SUDS is a visual analog scale in which the participants rate their anxiety/fear based on a range between 0 (*no anxiety/fear*) and 100 (*very severe anxiety/fear*). Refer to appendix B. A SUDS rating will be collected at the end of each video segment, reflecting maximum distress experienced during the viewing. An average of maximum distress ratings will be calculated for all segments viewed at a single time.

**Dental Fear Survey (DFS; Kleinknecht, Klepac, & Alexander, 1973).** The DFS consists of 20 self-report items that measure anxiety in regard to dental situations. Refer to appendix C. The measure examines physiological and behavioral responses to specific dental circumstances and situations, and contains three subscales. The subscales assess dental avoidance and anxiety, fear of dental stimuli/procedures, and arousal associated with dental

treatment. The DFS is rated on a 5-point Likert-type scale assessing how much of the responses (i.e., behavioral & physiological) occur in dental situations or the level of anxiety felt within the specific situations. The DFS has a total score of 100, and higher scores reflecting more anxiety felt with dental care-related fear (Kleinknecht et al., 1973).

DFS scores reflect general dental care-related fear and anxiety. The DFS has been widely utilized in behavioral dentistry research due to low demand on the participant in regard to time and cognitive requirements. The specific situations allow for individually measuring the participants' dental care-related fears. Furthermore, the DFS has demonstrated reliability (test-retest  $r = .88$ ) and validity ( $\alpha$ 's ranging from 75 to 95; McGlynn, McNeil, Gallagher, & Vrana, 1987; Smith & Moore, 1995; Heaton, Carlson, Smith, Baer, & Leeuw, 2007).

#### **IGroup Presence Questionnaire (IPQ; Schubert, Friedmann, & Regenbrecht, 2001).**

The IPQ is a 13-item questionnaire that measures the subjective report of *presence* within a virtual environment. Refer to appendix D. Three subscales make up the IPQ: spatial presence, involvement, and realness. The IPQ is rated on a Likert-type scale ranging from 0 to 6, and contain a variety of anchors (e.g., *fully disagree* to *fully agree*, *not at all* to *very much*). Psychometrics for the IPQ has been demonstrated to be sound, and the factor structure, across many samples, has been replicated (Schubert et al., 2001).

#### **Abbreviated acceptability rating profile (AARP; Tarnowski & Simonian, 1992).**

The AARP consists of 8-items that assess acceptability of treatment. Refer to appendix E. Items are rated on a 6-point Likert-type scale ranging from 1 (*strongly disagree*) to 6 (*strongly agree*). Good psychometrics have been demonstrated with the AARP (Cronbach's alpha ranging from .93 to .97; Caporino & Karver, 2012; Tarnowski & Simonian, 1992). The AARP was slightly modified to fit the current study.

**Dental Behavior Avoidance Test (DBAT).** In a laboratory furnished to exemplify a dental operatory, the DBAT will be conducted, consistent with prior research by McNeil, McGlynn, Cassisi, and Vrana (1989). The DBAT will consist of eight steps that simulate a dental examination, and each step will last up to 60 seconds. Escape from, or avoidance of, each step will be allowed, and will constitute a measure of escape/avoidance (i.e., total number of seconds of escape/avoidance behavior). A researcher will portray the dentist, and an undergraduate research assistant will portray the dental assistant. A maximum-distress SUDS rating will be reported by the participants at the end of each step of the DBAT. Throughout the procedure, participants' heart rate will be measured using a computer that controls a Coulbourn Instrument to measure ECG data. A four minute baseline will be recorded prior to the start of the DBAT. Before initiating the next step in the procedure, there will be a 60 second baseline recording.

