### **Participants**

G\*Power 3, a power analysis program, developed by Faul, Erdfelder, Lang, and Buchner (2007), was used to determine sample size. In order to achieve a power of  $\phi = .80$  with two measurements and three groups at a medium effect size of .25, the analysis suggests a total sample size of at least 36 participants. Inclusion for participation will include fluency in the English language, being 18 years of age or older, own or have access to a mobile phone, and report discomfort with dental related care. The participants will receive a compensation of \$40.00 upon completion of the study. This study will adhere to the guidelines presented by the

American Psychological Association for treatment of human research participants. In order to participate, subjects will be required to sign an informed consent statement that will be approved by the West Virginia University Institutional Review Board.

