### **Procedure**

The participants in the study will be recruited through advertisements in local newspapers, posted flyers on the campus of West Virginia University, and advertised on Craigslist (e.g., a website that provides services/goods). Upon arrival to the study, participants will be given a written informed consent form and information on study procedures. The researchers will discuss the process of the study and what is expected of the participant. The participants will be informed that they will receive \$40.00 for compensation at the completion of the study. After agreement to enlist in the study and completion of the ADIS-5, the participants will be randomly assigned to group (i.e., 2-week waitlist or treatment group) by previously prepared sealed opaque envelopes, complete the demographic questionnaire, conducted the DBAT, and answer the DFS. The researchers will then provide a 15-minute demonstration on how to conduct self-directed exposure therapy on the participant's mobile phone, and how to rate

SUDS. The researchers will describe that watching the exposure video three times per day is the ideal, one time per day is the suggested minimum, and viewing the exposure video five times per day is the suggested maximum.

The video will display a typical preventive visit to the dentist, including walking into the dental office, being called back for treatment by the dental assistant, sitting in the dentist chair, and seeing the dentist perform a teeth cleaning. The video will be 15-minutes in length, and be recorded by the researchers in both first- and third-person perspective. The actors in the video will be confederates and have knowledge about the purpose of the video. The actors in the video are from the School of Dentistry at West Virginia University.

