Proposed Analyses

Rates of procedure adherence (i.e., watching the video at least three times daily) will be assessed in order to examine the study's first question. The second question will be assessed by examining participants' rating of acceptability on the AARP with using a mobile phone as a method for self-directed exposure.

There will be 3 (group) x 2 (assessment) mixed measures analyses of variance (ANOVAs) which will be conducted to assess the first hypothesis regarding treatment effectiveness, with the DFS, and various DBAT measures (i.e., avoidance/escape, cardiac response, and SUDS verbal reports) as dependent variables. Sensitivity analyses will be conducted for baseline measurements. In order to examine the second hypothesis, a paired sample *t*-test assessing the relation of video perspective and scores on the PQ will be conducted.

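### If many participants show no DBAT avoidance at baseline, the mixed ANOVA on raw seconds loses much of its power for that outcome; a baseline-adjusted ANCOVA should be pre-specified for it

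*Protocol*

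**What the plan says.** - **Outcome.** Protocol, Dental Behavior Avoidance Test (DBAT): "The DBAT will consist of eight steps that simulate a dental examination". Each step lasts at most 60 s and the participant may escape or avoid any of them. What they avoid is totalled as "a measure of escape/avoidance (i.e., total number of seconds of escape/avoidance behavior".
- **Entry.** Protocol, Participants: apart from language, age and phone access, participants need only "report discomfort with dental related care". No minimum Dental Fear Survey (DFS) or DBAT score is set. The ADIS-5 interview only describes the sample.
- **Analysis.** SAP, Proposed Analyses: 3 (group) x 2 (assessment) "mixed measures analyses of variance (ANOVAs) which will be conducted to assess the first hypothesis". The dependent variables are the DFS and three DBAT measures: avoidance/escape, cardiac response and SUDS. No transformation, rank method or handling of a floor is given. Baseline appears only in an undefined sensitivity analysis.
- **Sample size.** Protocol, Participants: "a total sample size of at least 36 participants" for power .80 "with two measurements and three groups at a medium effect size of .25". The calculation is not tied to any outcome.

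**The concern.** Anyone who sits through the whole mock examination scores exactly 0, and nothing at entry screens such people out. A participant at 0 at baseline can only stay there or get worse, so cannot show benefit. The remaining scores are skewed, and a few large ones drive both the mean and the variance.

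With two assessments, the group-by-assessment test is a one-way F test on change scores, which fixes the slope of follow-up on baseline at 1. When exposure pushes many follow-up scores to the floor, that slope is too steep and the change score carries unnecessary noise.

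At stake is the only behavioural outcome for the first hypothesis. If zeros are common, a real reduction in avoidance could be reported as no effect.

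**Working it through.** **Inputs from the documents.** N = 36; three groups; two assessments; f = .25; score range 0 to 8 x 60 = 480 s.

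**Assumed, because not stated.** Alpha .05; allocation 12/12/12 (waitlist and two exposure orders), with 18/9/9 as an alternative; no dropout; pre-post correlation; zero share; spread of seconds.

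**1. The plan's own figure, with no floor.** Repeated-measures noncentrality is N f² m/(1 − ρ), with m = 2.
- ρ = .5: 36 x .0625 x 2/.5 = 9. The assessment effect (1 and 33 df) has power .829, which reproduces 36. The interaction (2 and 33 df), which the first hypothesis needs, has .729 and would need 42.
- ρ = .6: noncentrality 11.25, interaction power .826.
- ρ = .7: noncentrality 15, interaction power about .92.

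**2. Effect size in the simulation.** If both exposure groups shift by d SD and waitlist does not, the interaction f is d/√18. With d = 1.06, f = 1.06/4.243 = .25, so the simulated effect is the plan's own effect on the latent scale.

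**3. Adding the floor.** Baseline and follow-up tendencies are bivariate normal with correlation .7. Seconds = min(480, max(0, 250 x (z − c))), with c set by the baseline zero share. Both exposure groups shift by −1.06 at follow-up. Each analysis is a 2-df group F test at .05. Power with 12/12/12:

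| Baseline zeros | Planned ANOVA | Linear ANCOVA | Rank ANCOVA |
|---|---|---|---|
| 20% | .70 | .86 | .86 |
| 40% | .43 | .72 | .76 |
| 60% | .22 | .48 | .58 |
| 80% | .08 | .13 | .27 |

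At 10% zeros the planned test has .80 and linear ANCOVA .88. Repeat runs differ by about .02.

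**4. Another form of effect.** Exposure cuts follow-up seconds to 25% and leaves zeros at zero:

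| Baseline zeros | Planned ANOVA | Linear ANCOVA | Rank ANCOVA |
|---|---|---|---|
| 20% | .78 | .98 | .73 |
| 40% | .43 | .77 | .30 |
| 60% | .21 | .40 | .10 |

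With seconds halved at 40% zeros: .22, .33, .13.

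**5. Other settings (planned, linear, rank).**
- 18/9/9, shift model: .49, .70, .78 at 40% zeros; .26, .38, .57 at 60%; .10, .05, .16 at 80%.
- Correlation .5, 50% zeros: .25, .51, .60 for clipped-normal scores with 150 s per SD; .15, .36, .60 for right-skewed scores.
- Shift of 0.5 SD, 40% zeros: .19, .25, .24.

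**6. Type I error** (correlation .5, 30-70% zeros): planned ANOVA .025-.048, linear ANCOVA .026-.048, rank ANCOVA .049-.051. Both tests on raw seconds become conservative when scores are skewed and zeros are many.

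**The case against.** The strongest reply is that the premise is assumed. The documents give no zero share, mean or SD for DBAT seconds, and the research questions speak of phobic individuals. At 10% zeros the planned test keeps about .80. This stands: the loss is conditional.

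Second, a reader might infer that the shape of the score calls for replacing the ANOVA with a rank analysis. The calculations do not support that. Most of the gain at 40% zeros comes from baseline adjustment (.43 to .72), and ranking adds little (.72 to .76). If exposure shortens avoidance without abolishing it, rank ANCOVA falls below the planned test. The documents do not say which form of effect to expect.

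Third, it is tempting to add that ranks cost nothing when zeros are rare. The 250 s per SD model cannot show this cleanly: 480/250 = 1.92 SD, so at 2% zeros about 55% of baseline scores sit at the 480 s ceiling. With 150 s per SD and 2% zeros the three tests are close (.90, .93, .91).

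Fourth, avoidance is one of four dependent variables, none is named as primary, and this floor does not touch the DFS. That limits the consequence. The SAP's baseline sensitivity analysis does not answer the point, since it names neither a model nor an outcome.

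**Conclusion.** The point holds in conditional form. The 0-480 s range, the lenient entry criterion and the absence of floor handling are in the documents or follow directly from them. A large zero share is a reasonable inference from the entry criterion, not a documented fact. A reader might conclude that many scores will be 0 and that the planned test has little power. The documents do not establish either.

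Under the assumptions shown, the planned test's power falls from about .92 with no floor to .43 at 40% zeros and .22 at 60%. Linear ANCOVA recovers part of this (.72 and .48). With 12/12/12 it matched or beat the planned test under both forms of effect from 2% to 60% zeros. The gain shrinks with a smaller effect. At about 80% zeros no method has useful power, and with 18/9/9 linear ANCOVA is then below the planned test (.05 against .10). The consequence is confined to one outcome, but the remedy is cheap enough to recommend.

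**What to change.** In SAP, Proposed Analyses, take avoidance/escape out of the common mixed ANOVA and state:

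- **Main analysis of avoidance.** ANCOVA of week-2 avoidance seconds on group, adjusting for baseline seconds. Because of skew, a p-value from permuting group labels, following the allocation scheme used, may be preferred. The effect remains a mean difference in seconds.
- **Sensitivity analysis.** Rank ANCOVA (ranked week-2 on ranked baseline seconds), pre-specified and not the sole test. It gains when exposure moves avoiders to 0 (.58 against .48 at 60% zeros) and loses when exposure only shortens avoidance (.30 against .43 for the planned test at 40% zeros).
- **Description.** The share with any avoidance and the median seconds, by group and visit, so that readers can see how strong the floor was.

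The cost is SAP wording and a little more analysis. No new data or participants are needed, since baseline seconds are already collected. The SAP should add that the gain depends on the zero share, the size and form of the effect, and the allocation.

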### **Procedure**

The participants in the study will be recruited through advertisements in local newspapers, posted flyers on the campus of West Virginia University, and advertised on Craigslist (e.g., a website that provides services/goods). Upon arrival to the study, participants will be given a written informed consent form and information on study procedures. The researchers will discuss the process of the study and what is expected of the participant. The participants will be informed that they will receive \$40.00 for compensation at the completion of the study. After agreement to enlist in the study and completion of the ADIS-5, the participants will be randomly assigned to group (i.e., 2-week waitlist or treatment group) by previously prepared sealed opaque envelopes, complete the demographic questionnaire, conducted the DBAT, and answer the DFS. The researchers will then provide a 15-minute demonstration on how to conduct self-directed exposure therapy on the participant's mobile phone, and how to rate

SUDS. The researchers will describe that watching the exposure video three times per day is the ideal, one time per day is the suggested minimum, and viewing the exposure video five times per day is the suggested maximum.

The video will display a typical preventive visit to the dentist, including walking into the dental office, being called back for treatment by the dental assistant, sitting in the dentist chair, and seeing the dentist perform a teeth cleaning. The video will be 15-minutes in length, and be recorded by the researchers in both first- and third-person perspective. The actors in the video will be confederates and have knowledge about the purpose of the video. The actors in the video are from the School of Dentistry at West Virginia University.

Participants in the treatment group will receive daily text messages as a reminder to conduct the exposure. Participants will be asked to follow the link and sign in each day with their mobile phones. Before each exposure video, the participants will rate expected distress on the SUDS. Then the participants will be asked to watch a video depicting dental care-related phobic material. After viewing the exposure video, participants will rate actual distress experienced on the SUDS. The participants will then be prompted to watch the video again. If the participant decides to view the video again, they will go through the same procedure of pre-rating fear and anxiety, watching the video, and post-rating fear and anxiety. Finally, the participants will be prompted to complete the procedure once more. After completing the procedure three times, the participants will no longer be prompted, however, they have the ability to complete the procedure two more times if they so desire.

The participants in the treatment group will be randomly assigned by previously prepared sealed opaque envelopes to video content (i.e., first- or third-person perspective). After 1-week of first or third video perspective, the participants will be assessed by the researcher via

telephone. Questions on the PQ and the DFS will be answered by the participants. After the assessment, participants in the first-person perspective will be informed that the video content will change to third-person perspective. Participants in the third-person condition will be informed that the video content will change to first-person perspective. At the end of the two weeks, participants will be asked to return in person for a follow-up and to receive \$40.00 compensation. The follow-up assessment will consist of the DBAT, completing the DFS, answering the PQ, and rating acceptability of using a mobile phone as a mean of self-directed exposure.

The control group will be assessed on the DFS after one week via telephone. After the two weeks the participants in the control group will be asked to return for a follow-up assessment and receive \$40.00 compensation. The assessment will consist of the same as the treatment group. At the follow-up session, participants in the control group will be offered the same treatment, for ethical reasons, as the experimental group, however, the data will not be analyzed.

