## **Study Protocol**

The proposed study will examine the question of whether phobic individuals will use a mobile phone in self-directed exposure therapy. A second question is whether phobic participants will find the use of a mobile phone as an acceptable means of conducting self-directed exposure therapy.

Accompanying these two research questions are additional specific hypotheses. The first hypothesis is that filmed exposure stimuli, available on a mobile phone, will be associated with greater fear reduction in a self-directed exposure group relative to a control group. The second hypothesis is that greater presence will be reported with first-person perspective versus third-person perspective.

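### The ADIS-5 phobia result is available before allocation, but neither the envelopes nor the hypothesis 1 model uses it, so in a trial of about 36 the phobic share may differ noticeably between waitlist and treatment by chance

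*Protocol*

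**What the plan says.** - **Target and entry.** The Protocol's opening section poses "the question of whether phobic individuals will use a mobile phone in self-directed exposure therapy". The only fear-related entry condition (Protocol, Participants) is that people "report discomfort with dental related care". No DFS cut-off or diagnosis is required.
- **Role of the ADIS-5.** Only its specific phobia section is given. "The ADIS-5 will be conducted by clinicians in training", and the result is to "be used in order to describe the study's sample".
- **Timing.** Protocol, Procedure places allocation "After agreement to enlist in the study and completion of the ADIS-5". The baseline DBAT and DFS are listed after assignment, so as written the ADIS-5 is the only severity measure in hand when the envelope is opened.
- **Allocation.** "the participants will be randomly assigned to group (i.e., 2-week waitlist or treatment group) by previously prepared sealed opaque envelopes". Treated participants are then "randomly assigned by previously prepared sealed opaque envelopes to video content". Neither description mentions strata, blocks or a ratio.
- **Size.** From the power calculation, "the analysis suggests a total sample size of at least 36 participants".
- **Analysis.** The SAP tests hypothesis 1 with three-group by two-assessment mixed ANOVAs on the DFS and DBAT measures. There is no ADIS-5 term. One sentence promises sensitivity analyses of baseline measures, without naming variables or a method.

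**The concern.** Hypothesis 1 compares fear reduction between small groups. People with a diagnosable phobia may change by a different amount from people with mild discomfort, for example because the latter have little room to fall on the DFS or on DBAT escape time. If one arm happens to hold clearly more phobic participants, part of any difference in change, or of its absence, could be put down to case mix. With about 12 people per group, that could not be settled convincingly afterwards. The information needed to limit the problem is collected just before allocation and then used only descriptively.

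**Working it through.** **1. The plan's own figure.** Inputs from Protocol, Participants: f = 0.25, power 0.80, three groups, two measurements. Assumed, because not stated: alpha 0.05, correlation 0.5 between assessments, no dropout. With lambda = f² × N × m / (1 − rho) = 0.0625 × 36 × 2 / 0.5 = 9.0, the within-subject (time) test on 1 and 33 df has power 0.829, and 36 is the smallest multiple of three that reaches 0.80. So 36 is reproduced for the time effect. The group-by-assessment interaction needs 42 at the same correlation. That is a separate matter and nothing below depends on it.

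**2. Inputs for imbalance.** N = 36 (Protocol). The split is not given: I use 18:18 (two groups, as in Procedure) and 12:24 (three equal groups, two of them treated). The number phobic, K, is not given: I use 4 to 32 of 36.

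**3. Formula.** With fixed group sizes and no stratification, the phobic count x in the waitlist arm is hypergeometric. The gap is |x/n1 − (K − x)/n2|.

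- 18:18, K = 18: gaps move in steps of 11.1 points, and a gap under 20 points needs x = 8, 9 or 10. P(gap ≥ 20) = 1 − (0.211 + 0.2605 + 0.211) = 0.318.
- 12:24, K = 18: gaps move in steps of 12.5 points, and a gap under 20 points needs x = 5, 6 or 7. P(gap ≥ 20) = 1 − (0.2178 + 0.2753 + 0.2178) = 0.289.

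| Phobic of 36 | 18:18, ≥20 pts | 12:24, ≥20 pts | 18:18, ≥30 pts | 12:24, ≥30 pts |
|---|---|---|---|---|
| 4 (or 32) | 10.4% | 9.8% | 0% | 0.8% |
| 9 (or 27) | 12.1% | 21.9% | 1.8% | 3.6% |
| 12 (or 24) | 28.9% | 26.0% | 7.5% | 5.8% |
| 18 | 31.8% | 28.9% | 9.4% | 7.5% |

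Because gaps come in steps, some counts between these rows fall outside the 20-point range. With 18:18 and K = 5 (or 31), only an all-or-none split reaches 20 points: 2 × C(18,5) / C(36,5) = 2 × 8,568 / 376,992 = 4.5%. K = 7 (or 29) gives 2 × (31,824 + 334,152) / 8,347,680 = 8.8%. No other count from 4 to 32 falls below about 10% or exceeds 32%, and none exceeds 10% for 30 points.

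**4. Cross-checks.** Unrestricted 1:1 randomisation gives 24% for a gap of 20 points or more at K = 18. With three groups of 12, the largest of the three pairwise gaps is at least 25 points in about 53% of allocations at 50% prevalence and 43% at 25%. At N = 200, 1:1, the 20-point figure falls to 0.7%, so this is a small-trial problem.

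**5. What a gap could do to the result.** Suppose phobic and non-phobic change scores differ by d SD (assumed). A 25-point gap shifts the treatment contrast by 0.25d: 0.125 SD at d = 0.5 and 0.20 SD at d = 0.8. The standard error of the contrast at 12:24 is √(1/12 + 1/24) = 0.35 SD. At 50% prevalence, phobia status would account for 0.25 × d² of the variance of change: 6% at d = 0.5 and 16% at d = 0.8.

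**6. After stratifying.** The gap is then limited to what an incomplete last block can leave. With two arms of 18, blocks of 2 leave at most 1/18 = 6 points and blocks of 4 at most 2/18 = 11 points. With three groups of about 12, blocks of 3 leave at most about 1/12 = 8 points and blocks of 6 at most about 2/12 = 17 points in the worst case.

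**The case against.** A reader might infer that the comparison is biased or the test invalid. The documents do not support that. Allocation is random and by sealed opaque envelopes, so chance imbalance averages out and the usual standard error already allows for it. In step 5 the shift is well inside one standard error.

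A reader might also infer that a more phobic arm would fall further simply because it starts higher. The pre-post model removes a constant baseline offset, so only a difference in change matters. Regression to the mean is not shown either: nobody is selected on a DFS or DBAT cut-off, and a more phobic group has a higher true mean.

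The size depends on threshold and prevalence. At 12:24 with 12, 18 or 24 phobic, a cut-off of 25 points gives 26% to 29%, but that counts gaps of exactly 25 points; above it the figure is 5.8% to 7.5%. With 4 of 36 phobic, a gap of 25 points or more occurs in under 1%.

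The remaining objections also have force. Covariate adjustment can recover much of the precision without restoring balance. Nothing in the documents shows that phobia status predicts change. The interviewers are clinicians in training, and psychometric support is cited only for earlier ADIS versions. Hypothesis 2 is a paired comparison, so imbalance between video orders matters little there. That the envelopes take no account of the ADIS-5 is inferred from silence, although its stated descriptive role supports the inference.

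All of this limits the point without removing it. The SAP's sentence on baseline measures is too unspecific to count as ADIS-5 adjustment, and a cheap use of information already in hand is left out.

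**Conclusion.** The point stands as an inexpensive improvement to design and analysis. A gap of 20 points or more in phobic share between waitlist and treatment would arise in about 10% to 32% of randomisations at the tabulated counts (down to 4.5% at a few others with 18:18), and a gap of 30 points or more in under 10%. These figures rest on N = 36, fixed splits of 18:18 or 12:24, and 4 to 32 phobic participants, of which only the 36 comes from the documents. The consequence is some loss of precision and a weaker interpretation of hypothesis 1, and only if phobia status predicts change.

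**What to change.** 1. Prepare two concealed envelope sets, one for participants who meet the ADIS-5 specific phobia (dental) diagnosis and one for those who do not. Use small permuted blocks of varying size across the three groups (waitlist, first-then-third person, third-then-first person), and keep the block sizes from enrolling staff. Score the ADIS-5 section before the envelope is opened and draw from the matching set.
2. Prespecify in the SAP that the hypothesis 1 models include the ADIS-5 stratum and its interaction with assessment, so that the term acts on change and not only on level.
3. If envelopes are already in use, adding the ADIS-5 term before outcome data are examined is the minimum.

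Cost: a second envelope set and same-visit scoring of an interview already done, with no extra visit, staff or procedure. The model loses about one degree of freedom (33 to 32 for the test of change at N = 36). Each stratum may end on an incomplete block. Some misclassification by trainee interviewers would reduce the benefit without harming validity.

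### Random assignment is listed before the baseline DBAT and DFS, and nothing in the available text withholds group until they are complete

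*Protocol*

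**What the plan says.** The Procedure section of the Protocol sets out the first visit in one sentence. Consent and the ADIS-5 come first. Next, "the participants will be randomly assigned to group (i.e., 2-week waitlist or treatment group". The rest of that sentence gives the method of assignment and the steps listed after it: "by previously prepared sealed opaque envelopes, complete the demographic questionnaire, conducted the DBAT, and answer the DFS". The sentence that follows reads "The researchers will then provide a 15-minute demonstration on how to conduct self-directed exposure therapy". Instruction in SUDS rating is named there as part of the same demonstration, in the words "mobile phone, and how to rate".

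The DBAT paragraph says "A researcher will portray the dentist, and an undergraduate research assistant will portray the dental assistant". Participants may escape or avoid any step, and the seconds of doing so are an outcome. It also says "A maximum-distress SUDS rating will be reported by the participants at the end of each step of the DBAT".

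Later in the Procedure there is a second envelope: "The participants in the treatment group will be randomly assigned by previously prepared sealed opaque envelopes to video content". When it is opened relative to baseline is not stated. The same section offers the waitlist group the treatment at the follow-up session.

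The SAP (Proposed Analyses) tests hypothesis 1 with 3 (group) x 2 (assessment) mixed ANOVAs on the DFS and the DBAT measures. It adds that baseline measurements will have sensitivity analyses, without naming any.

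**The concern.** Sealed opaque envelopes conceal the allocation until they are opened, and not after that. If the envelope is opened where the sentence puts it, a participant who has just learned that they are on the waitlist, or about to start exposure, then fills in the DFS, rates distress and decides how long to tolerate each DBAT step. The staff playing dentist and assistant may know the group too. The DFS and SUDS are self-reports and avoidance is voluntary, so all three are open to this influence. Cardiac response is left out: "A four minute baseline will be recorded prior to the start of the DBAT", but how heart rate is scored against that and the between-step recordings is not defined.

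The ANOVAs for hypothesis 1 use these values as one of their two assessments. A baseline shift that fades by follow-up appears as differential change. On measures where a higher score is worse, a raised waitlist baseline then works against the treatment; a raised treatment-group baseline, or a lowered waitlist baseline, favours it.

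**Working it through.** **1. Order of events.** The listed sequence is consent, ADIS-5, group assignment, demographics, DBAT, DFS, demonstration. Only consent and the ADIS-5 precede assignment, and the Protocol uses the ADIS-5 to describe the sample, not as an outcome. Every baseline outcome therefore comes after assignment. No sentence in either document says that the envelope stays closed, or that participants or DBAT staff are unaware of group, at baseline.

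**2. Two related points in the same text.**
- The only stated teaching of SUDS rating comes in the demonstration, after a DBAT that needs a rating at every step. This affects all groups and is not a group-knowledge bias.
- The demonstration is not limited to the treatment group, although the waitlist group is offered treatment only at follow-up.

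**3. Bias of each analysis.** Let one group's baseline be shifted by s (in SDs), let a fraction p of the shift remain at follow-up, and let rho be the pre-post correlation. SDs are equal at both times and there is no true effect. The bias in that group's contrast with the others is:
- change (the group x assessment interaction): sp - s = s(p - 1), zero only if p = 1;
- follow-up only: sp, zero only if p = 0;
- adjusted for the affected baseline (ANCOVA): sp - rho s = s(p - rho), zero only if p = rho.

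No analysis is unbiased without knowing p, so an unnamed baseline sensitivity analysis does not prevent or repair the problem.

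**4. Illustration of size.** From the documents: 36 participants in total (Participants section) and DFS test-retest r = .88 (Dental Fear Survey paragraph). Assumed: 12 per group, alpha .05, rho = .5 as an alternative to .88, and s = 0.2 or 0.3 SD. The documents give no value for s.

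With two assessments the interaction test is a one-way ANOVA on change, F(2, 33), critical value 3.285. The variance of change is 2(1 - rho). With one of three equal groups shifted, the noncentrality is

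lambda = 12 x (2/3) x [s(1 - p)]^2 / [2(1 - rho)] = 8[s(1 - p)]^2 / [2(1 - rho)].

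For p = 0:

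| s (SD) | rho | lambda | Type I error |
|---|---|---|---|
| 0.2 | .5 | 8 x 0.04 / 1.00 = 0.32 | 7.3% |
| 0.3 | .5 | 8 x 0.09 / 1.00 = 0.72 | 10.3% |
| 0.2 | .88 | 8 x 0.04 / 0.24 = 1.33 | 15.2% |
| 0.3 | .88 | 8 x 0.09 / 0.24 = 3.00 | 29.7% |

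If half the shift persists (p = .5), lambda falls to a quarter. At rho = .5 the error is then 5.6% and 6.3%. If all of it persists, the error is 5%.

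**5. Sensitivity to the split.** The Procedure could also be read as 18 waitlist and 9 per video order. If the group of 18 is the one shifted, the multiplier 8 becomes 18 x 18/36 = 9. For s = 0.3, rho = .5 and p = 0, lambda is 0.81 and the error is 11% instead of 10%.

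**The case against.** The evidence is one loosely drafted sentence whose items are joined by commas; the word marking sequence appears only before the demonstration. Figure 1, cited under Experimental Design as the study flowchart, was not available and may show baseline first. This stands as a limit on certainty. A reader might infer that group was in fact known at baseline, or that the trial's baseline is biased. The documents support neither: they show an order that permits it and no statement that prevents it.

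The size of the shift is assumed, so the percentages show what could happen and do not estimate what will. This also stands. With a small shift, or one that mostly persists, the inflation is slight.

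The weightiest objection is that participants know their group at follow-up under any order of the first visit, since one arm watches videos and the other waits. A reader might infer that reordering removes the effect of group knowledge from the comparison. It does not. If knowing one's group shifted responses equally at both visits, the listed order would leave the change analysis unbiased, and measuring baseline first would leave the follow-up part of the shift in it. That part is ordinary bias from an unblinded outcome and is not caused by the listed order. An uncontaminated baseline is still the right starting point, because a baseline shift of unknown persistence cannot be separated out afterwards.

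**Conclusion.** The point holds in conditional form and should be fixed. As listed, assignment precedes every baseline outcome, and no available text withholds group until the DFS is complete. If that order is followed, baseline DFS, DBAT SUDS and avoidance are exposed to knowledge of group, with unknown size and direction, and the SAP's unspecified sensitivity analyses do not prevent it.

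On the stated assumptions, the inflation of type I error runs from none (full persistence) to about 30% (0.3 SD, no persistence, correlation .88). The lower correlation of .5 gives about 7% to 10% for non-persistent shifts of 0.2 to 0.3 SD. The .88 is a test-retest reliability for the DFS only; its use as the pre-post correlation in this trial is itself an assumption. Confidence is medium, because the drafting is loose and Figure 1 could settle the order. The case for changing the text rests on the listed sequence and the low cost of changing it, not on these percentages.

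**What to change.** **Before enrolment.** Restate the first visit so that consent, the ADIS-5, the demographic questionnaire, an explanation of the SUDS, and the baseline DBAT and DFS are all completed first. Only then are the envelopes for group and, in the treatment group, for video order opened. Alternatively, keep the text and state that the envelopes stay unopened until the DFS is complete. Check that Figure 1 agrees.

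Separately, reconcile the parts of the Procedure that leave open whether the waitlist group receives the demonstration at the first visit or only when treatment is offered at follow-up.

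The cost is essentially nil: the same visit, measures and sample size, with a sentence or two rewritten.

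**If participants have already been enrolled in the listed order.** Add to the SAP a follow-up-only comparison of the randomised groups, as a sensitivity analysis beside the change analysis and not in its place. If one group's baseline was shifted and part of the shift persists (p between 0 and 1), the biases s(p - 1) and sp have opposite signs, so in expectation the two estimates bracket the true effect. For s = 0.3 and p = .5 they are -0.15 and +0.15 SD. State that this reading fails if the shift at follow-up is larger than at baseline or reversed, and that any single pair of estimates also carries sampling error. The cost is one added analysis and a statement of its limits.
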